5. BASELINE CHARACTERISTICS

5.1. Demographics

Subject demographic variables (ie, age, sex, race, and ethnicity) will be summarized for Safety Analysis Set using descriptive statistics for age, and using number and percentage of subjects for sex, race, and ethnicity.

A by-subject demographic listing, including the informed consent date, will be provided by subject ID number in ascending order for All Enrolled Analysis Set.

5.2. Other Baseline Characteristics

Other baseline characteristics include body weight (in kg), height (in cm), body mass index (BMI; in kg/m²), and ECOG status. BMI will be calculated by the formula:

$$\text{BMI (kg/m}^2\text{)} = \text{weight} / (\text{height}^2) \text{ (round to 1 decimal point).}$$

Other baseline characteristics will be summarized by cohort and overall using descriptive statistics for continuous variables and using number and percentage of subjects for categorical variables. The summary of demographic and baseline characteristics data will be provided for the Safety Analysis Set.

A by-subject listing of other baseline characteristics will be provided by subject ID number in ascending order for All Enrolled Analysis Set.

5.3. Medical History

Medical history will be collected at screening for disease-specific conditions including solid tumor malignancy status, and general conditions (i.e. conditions not specific to the disease being studied).

A by-subject listing of disease-specific medical history will be provided by cohort and subject ID number in ascending order.

General medical history data will not be coded but will be listed only. A by-subject listing of general medical history will be provided by cohort and subject ID number in ascending order.

5.4. Prior Anti-Cancer Therapy

The details of prior anti-cancer therapy will be listed by cohort and subject ID number in ascending order.

5.5. Prior and On Study Radiotherapy

The details of all radiotherapy will also be listed by cohort and subject ID number in ascending order.

5.6. Surgeries and Procedures

A by-subject listing of prior and on-study surgeries and procedures will be provided by cohort and subject ID number in ascending order.

7. ANALYSIS OF ADVERSE EVENTS AND LABORATORY EVALUATIONS

All Adverse Events (AEs) will be listed. The focus of AE summarization will be on treatment-emergent adverse events (TEAEs). Safety analyses will be conducted using Safety Analysis Set, unless otherwise specified.

7.1. Adverse Events and Deaths

7.1.1. Adverse Event Dictionary

Clinical and laboratory adverse events (AEs) will be coded using the current version of Medical Dictionary for Regulatory Activities (MedDRA). System organ class (SOC), high-level group term (HLGT), high-level term (HLT), preferred term (PT), and lower-level term (LLT) will be provided in the AE dataset.

7.1.2. Adverse Event Severity

Adverse events are graded by the investigator as Grade 1, 2, 3, 4, or 5 according to Common Terminology Criteria for Adverse Events (CTCAE) Version 5.0. The severity grade of events for which the investigator did not record severity will be categorized as “missing” for tabular summaries and data listings. The missing category will be listed last in summary presentation.

7.1.3. Relationship of Adverse Events to Study Drug

Related AEs are those for which the investigator selected “Related” on the AE CRF to the question of “Related to Study Treatment.” Relatedness will always default to the investigator’s choice, not that of the medical monitor. Events for which the investigator did not record relationship to study drug will be considered related to study drug for summary purposes. However, by-subject data listings will show the relationship as missing.

7.1.4. Serious Adverse Events

Serious adverse events (SAEs) will be identified and captured as SAEs if the AEs met the definitions of SAEs that are specified in the study protocol. SAEs captured and stored in the clinical database will be reconciled with the SAE database from then Gilead Global Safety Department before data finalization.

7.1.5. Treatment-Emergent Adverse Events

7.1.5.1. Definition of Treatment-Emergent Adverse Events

Treatment-emergent adverse events (TEAEs) are defined as 1 or both of the following:

- Any AEs with an onset date on or after the study drug start date and no later than 30 days after permanent discontinuation of study drug
- Any AEs leading to permanent discontinuation of study drug.

7.1.5.2. Incomplete Dates

If the onset date of the AE is incomplete and the AE stop date is not prior to the first dosing date of study drug, then the month and year (or year alone if month is not recorded) of onset determine whether an AE is treatment emergent. The event is considered treatment emergent if both of the following 2 criteria are met:

- The AE onset is the same as or after the month and year (or year) of the first dosing date of study drug, and
- The AE onset date is the same as or before the month and year (or year) of the date corresponding to 30 days after the date of the last dose of study drug.

An AE with completely missing onset and stop dates, or with the onset date missing and a stop date later than the first dosing date of study drug, will be considered to be treatment emergent. In addition, an AE with the onset date missing and incomplete stop date with the same or later month and year (or year alone if month is not recorded) as the first dosing date of study drug will be considered treatment emergent.

In case when the AE onset date is incomplete and needs to be imputed, the following algorithm will be followed:

- If the day is missing but the month and year are available, then the imputed day will be the first day of the month or the first dosing date if they have the same month and year, whichever is later.
- If the day and month are missing but year is available, then the imputed day and month will be 01Jan or the first dosing date if they have the same year, whichever is later.

7.1.6. Summaries of Adverse Events and Deaths

TEAEs will be summarized by cohort/dose level based on the Safety Analysis Set.

7.1.6.1. Summaries of Adverse Events Incidence by Severity

The number and percentage of subjects who experienced at least 1 TEAE will be provided and summarized by PT and severity in descending order of total frequency:

- Treatment-Emergent Adverse Events by PT and Severity

For the AE categories described below, summaries will be provided by PT in descending order of total frequency:

- Grade 3 or Higher Treatment-Emergent Adverse Events
- Treatment-Emergent GS-4224 related Adverse Events
- Treatment-Emergent Serious Adverse Events
- Treatment-Emergent GS-4224 related Serious Adverse Events
- Treatment-Emergent Adverse Events leading to discontinuation of GS-4224
- Treatment-Emergent Adverse Events leading to temporary interruption of GS-4224
- Treatment-Emergent Adverse Events leading to Death
- Treatment-Emergent Adverse Events leading to study discontinuation

A brief, high-level summary of AEs described above will be provided by cohort and by the number and percentage of subjects who experienced the above AEs.

For summaries of TEAEs by PT, multiple events will be counted only once per subject in each summary. Adverse events will be summarized and listed by PT in descending order of total frequency. For summaries by severity, the most severe severity will be used for those AEs that occurred more than once in a given subject during the study.

In addition, by-subject data listings will be provided by cohort and subject ID number in ascending order for the following:

- All AEs, indicating whether the event is treatment emergent
- All SAEs
- All Deaths
- All Adverse Events with Grade 3 or Higher
- All Adverse Events leading to discontinuation of GS-4224
- All Adverse Events leading to temporary interruption of GS-4224
- Adverse Events for Subject(s) with Intra-Subject Dose Escalation
- All Adverse Events leading to study discontinuation

A flag will be included in the listings to indicate whether the event is treatment emergent.

7.1.6.2. Summary of Deaths

A summary (number and percentage of subjects) of deaths will be provided by cohort. The summary will include the following categories:

- All deaths
- Deaths within 30 days of the last dosing of study drug
- Deaths beyond 30 days of the last dosing of study drug.

Every attempt will be made to ensure that complete death dates are recorded. In those rare instances where complete death dates are not recorded, the following algorithm will be used:

- If day is missing but the month and year are available, then the imputed date will be the 1st day of the month or the last known alive date + 1, whichever is later.

A by-subject listing of all deaths occurred during this study will be provided by cohort and subject ID number in ascending order.

7.1.7. Definition and Analysis of Dose Limiting Toxicity

Toxicity will be graded according CTCAE Version 5.0. A DLT is any toxicity specified in the study protocol occurring during the DLT assessment window (Day 1 through Day 21).

DLTs occurred within the 21-Day DLT observation period will be summarized by PT in descending order of total frequency for the DLT-Evaluable Analysis Set. Toxicities that meet the criteria of DLTs and occur beyond the first 21 days observation period (ie. DLT-type AEs) will also be summarized for the Safety Analysis Set by PT only in descending order of total frequency.

In addition, by-subject data listings will be provided by cohort and subject ID number in ascending order for the following:

- Dose Limiting Toxicities
- DLT-type AEs: toxicities that met the criteria of DLTs and occurred beyond the first 21 days observation period during study

7.2. Laboratory Evaluations

Laboratory data collected during the study will be analyzed and summarized using both quantitative and qualitative methods. Summaries of laboratory data will be provided for the Safety Analysis Set and will include data collected up to the last dose of study drug plus 30 days. The analysis will be based on values reported in conventional units. When values are below the LOQ, they will be listed as such, and the closest imputed value will be used for the purpose of calculating summary statistics as specified in Section 3.5.

A by-subject listing for all lab test results will be provided by cohort, subject ID number and time point in chronological order for hematology, serum chemistry, coagulation, endocrine function tests and urinalysis separately. Values falling outside of the relevant reference range and/or having a severity Grade of 1 or higher on the CTCAE severity grade will be flagged in the data listings, as appropriate.

No formal statistical testing is planned.

7.2.1. Graded Laboratory Values

CTCAE Version 5.0 will be used to assign toxicity Grades (0 to 4) to laboratory results for analysis. Grade 0 includes all values that do not meet the criteria for an abnormality of at least Grade 1. For laboratory tests with criteria for both increased and decreased levels, analyses for each direction (ie, increased, decreased) will be presented separately.

Local labs will be graded based on central lab normal ranges with in-house macro. Baseline grade will be based on central laboratory results, unless only local labs are collected prior to the first dosing of study drug. For post-baseline grade, the worst toxicity grade considering both central and local lab results will be used for the summary of lab toxicities. All central and local laboratory values will be listed for All Enrolled Subjects.

7.2.1.1. Treatment-Emergent Laboratory Abnormalities

Treatment-emergent laboratory abnormalities are defined as values that increase at least 1 toxicity grade from baseline at any postbaseline time point, up to and including the date of last dose of study drug plus 30 days for subjects who permanently discontinued study drug, or the last available date in the database snapshot for subjects who were still on treatment at the time of an analysis. A baseline laboratory value will be defined as the last measurement obtained on or prior to the date/time of first dose of study drug. If the relevant baseline laboratory value is missing, any abnormality of at least Grade 1 observed within the time frame specified above will be considered treatment emergent.

7.2.1.2. Summaries of Laboratory Abnormalities

The following summaries (number and percentage of subjects) for treatment-emergent laboratory abnormalities will be provided by lab test and cohort; subjects will be categorized according to the most severe postbaseline abnormality grade for a given lab test:

- TE laboratory abnormalities

In the summary of laboratory abnormalities, the denominator is the number of subjects with nonmissing postbaseline values up to 30 days after last dosing date.

7.3. Body Weight and Vital Signs

A by-subject listing of body weight and vital signs will be provided for All Enrolled Subjects by cohort subject ID number and visit in chronological order.

7.4. Prior and Concomitant Medications

Medications collected at screening and during the study will be coded using the current version of the World Health Organization Drug dictionary.

7.4.1. Prior Medications

Prior medications are defined as any medications begun before a subject took the first study drug.

For the purposes of analysis, any medication with a start date prior to the first dosing date of study drug will be considered as prior medication regardless of when the stop date is. If a partial start date is entered the medication will be considered prior unless the month and year (if day is missing) or year (if day and month are missing) of the start date are after the first dosing date. Medications with a completely missing start date will be considered as prior medication, unless otherwise specified.

All prior medications (other than per-protocol study drugs) will be provided in a by-subject listing sorted by cohort, subject ID number and administration date in chronological order based on All Enrolled Analysis Set.

7.4.2. Concomitant Medications

For the purposes of analysis, concomitant medications are defined as any medications

- started prior to or on the first dosing date of study drug and continued to be taken after the first dosing date, or
- started after the first dosing date but prior to or on the last dosing date of study drug.

Medications started and stopped on the same day as the first dosing date or the last dosing date of study drug will also be considered concomitant. Medications with a stop date that is prior to the date of first dosing date of study drug or a start date that is after the last dosing date of study drug will not be considered as concomitant medication.

If a partial stop date is entered, any medication with the month and year (if day is missing) or year (if day and month are missing) prior to the date of first study drug administration will not be considered as concomitant medication. If a partial start date is entered, any medication with the month and year (if day is missing) or year (if day and month are missing) after the study drug stop date will not be considered as concomitant medication. Medications with completely missing start and stop dates will be considered as the concomitant medication, unless otherwise specified.

All concomitant medications (other than per-protocol study drugs) will be provided in a by-subject listing sorted by cohort, subject ID number and administration date in chronological order based on All Enrolled Analysis Set.

7.5. Electrocardiogram Results

A standard 12-lead electrocardiogram (ECG) will be performed using local standard procedures at screening and at subsequent visits as specified in Appendix 2 of the protocol.

For ECG data, corrected QT (QTc) intervals will be derived using Fridericia's correction (QTcF) as follows:

$$QT_{cF} = \frac{QT}{\sqrt[3]{RR}}$$

where QT is measured in msec; RR = 60/Heart Rate (beats per min [bpm]) and RR is measured in seconds. Per Gilead data collection standard, ventricular rate (VR) is taken as heart rate and will be used to derive RR.

A by-subject listing of 12-lead ECG will be provided for All Enrolled Subjects by cohort, subject ID number and visit in chronological order.

7.6. Other Safety Measures

Eastern Cooperative Oncology Group (ECOG) performance status is an investigator assessment of the impact of the disease on the subject's activities of daily living. ECOG assessments will be performed at the time points listed in the Study Procedures Table (Appendix 2 of the protocol).

By-subject listings will be generated for the All Enrolled Analysis Set by cohort and subject ID number in ascending order for the following safety parameters and comments:

- ECOG performance scores
- General Comments

7.7. Changes from Protocol-Specified Safety Analyses

There are no deviations from the protocol-specified safety analyses.

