### 8.4. Data Handling Conventions

By-subject listings will be created for important variables from each eCRF module. Summary tables for continuous variables will contain the following statistics: N (number in analysis set), n (number with data), mean, standard deviation, 95% CIs on the mean, median, minimum, and maximum. Summary tables for categorical variables will include: N, n, percentage, and 95% CIs on the percentage. Unless otherwise indicated, 95% CIs for binary variables will be calculated using the binomial distribution (exact method) and will be 2-sided. Data will be described and summarized by cohort, analysis set, and time point.

The baseline value will be the last (most recent) pretreatment value before or on the first dosing date of study drug. As appropriate, changes from baseline to each subsequent time point will be described and summarized. Graphical techniques (eg, waterfall plots, Kaplan-Meier [KM] curves, line plots) may be used when such methods are appropriate and informative. Data from all sites will be pooled for all analyses. Analyses will be based upon the observed data unless methods for handling missing data are specified. If there is a significant degree of non-normality, analyses may be performed on log-transformed data or nonparametric tests may be applied, as appropriate.

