### **8.7.1. Extent of Exposure**

A subject's extent of exposure to study drug data will be generated from the study drug administration data. Descriptive information will be provided by cohort, indication and treatment regarding the number of doses of study drug prescribed, the total number of doses taken, the duration of exposure to study drug, and the number and timing of prescribed dose interruptions.

GS-4224 compliance will be described in terms of the proportion of study drug actually taken based on returned pill count relative to the amount that was dispensed (taking into account physician-prescribed interruptions).

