### **8.7.2. Adverse Events**

AEs will be coded using the Medical Dictionary for Regulatory Activities (MedDRA). System Organ Class (SOC), High-Level Group Term, High-Level Term, Preferred Term (PT), and Lower-Level Term will be attached to the clinical database. The severity of AEs will be graded by the investigator according to the NCI-CTCAE, version 5.0, whenever possible. If a NCI-CTCAE criterion does not exist for a specific type of AE, the grade corresponding to the appropriate adjective will be used by the investigator to describe the intensity of the AE: Grade 1 (mild), Grade 2 (moderate), Grade 3 (severe), Grade 4 (life threatening), or Grade 5 (fatal). The relationship of the AE to the study drug will be categorized as related or unrelated.

All AEs will be listed. The focus of AE summarization will be on TEAEs. A TEAE is defined as any AE with onset date on or after the date of first dose of study drug up to 30 days after permanent study drug discontinuation or any AEs leading to premature study drug discontinuation. Summaries (number and percentage of subjects) of TEAEs by SOC and PT will be provided by cohort, indication, and treatment.

Summary tables will be presented to show the number and percentage of subjects reporting TEAEs by severity grade and corresponding percentages. A subject who reports multiple TEAEs within the same PT (or SOC) is counted only once for that PT (or SOC) using the worst severity grade. Separate listings and summaries will be prepared for the following types of TEAEs:

- Study drug-related AEs
- AEs that are Grade  $\geq 3$  in severity
- AEs leading to study drug interruption and/or dose modification
- AEs leading to study drug discontinuation
- SAEs

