### 8.7.3. Laboratory Evaluations

Selected laboratory data will be summarized based on observed data. Data and change from baseline at all scheduled time points will be summarized. The focus of laboratory data summarization will be on treatment-emergent laboratory abnormalities. A treatment-emergent laboratory abnormality is defined as an abnormality that, compared to baseline, worsens by  $\geq 1$  grade in the period from the first dose of study drug to 30 days after the last dose of study treatment. If baseline data are missing, then any graded abnormality (ie, an abnormality that is Grade  $\geq 1$  in severity) will be considered treatment emergent.

Graded laboratory abnormalities will be defined using the NCI-CTCAE version 5.0 when applicable. Summary tables will be presented for each relevant assay to show the number of subjects by CTCAE severity grade with corresponding percentages. For parameters for which a CTCAE scale does not exist, the frequency of subjects with values below, within, and above the normal ranges will be summarized. Subjects will be characterized only once for a given assay, based on their worst severity grade observed during a period of interest (eg, during the study or from baseline to a particular visit).

Shift tables for selected laboratory data may also be presented by showing change in CTCAE severity grade from baseline to the worst grade after baseline. For parameters for which a CTCAE scale does not exist, shift tables presented will show change in results from baseline to the worst grade after baseline. Separate listings and summaries will be prepared for laboratory abnormalities that are Grade  $\geq 3$  in severity.

CCI

[Redacted]

CCI

[Redacted]

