3. GENERAL CONSIDERATIONS FOR DATA ANALYSES

Analysis results will be presented using descriptive statistics. For categorical variables, the number and percentage of subjects in each category will be presented; for continuous variables, the number of subjects (n), mean, standard deviation (StD) or standard error (SE), median, first quartile (Q1), third quartile (Q3), minimum, and maximum will be presented.

By-subject listings will be presented for all subjects in the All Enrolled Analysis Set and sorted by dose cohort, subject ID number, visit date, and time (if applicable). Data collected on log forms, such as AEs, will be presented in chronological order within the subject. The cohort to which subjects were initially assigned will be used in the listings. Age, sex at birth, race, and ethnicity information for each subject will be presented in the listings, as space permits.

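### SAP 7.7 declares the protocol's safety analyses unchanged, yet the SAP omits the exact 95% CI on DLT incidence, the primary endpoint, and reduces several other safety outputs

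*SAP*

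**What the plan says.** SAP 7.7 consists of one sentence: "There are no deviations from the protocol-specified safety analyses".

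Protocol 8.4 sets the general rule for tables: "Summary tables for categorical variables will include: N, n, percentage, and 95% CIs on the percentage". The same section also fixes the default method, which holds wherever the protocol states no other: "95% CIs for binary variables will be calculated using the binomial distribution (exact method) and will be 2-sided". Protocol 8.1.2 names DLT incidence in Phase 1b as the primary endpoint. Protocol 3.2.1 and SAP 1.2.1 define the MTD by the number of subjects with a DLT, 0 or 1 out of 6.

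For categorical variables SAP 3 says "the number and percentage of subjects in each category will be presented" and stops there. SAP 7.1.7 says that DLTs in the 21-day window "will be summarized by PT in descending order of total frequency for the DLT-Evaluable Analysis Set". It specifies a layout by cohort for the DLT listings, but not for this summary.

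SAP 1 explains that the study ended early in Phase 1b for lack of objective efficacy and that the SAP covers Phase 1b data only, for a synoptic CSR. SAP 2.1.2 and 2.1.3 each name an analysis that the protocol planned and say that early termination is why it will not be done.

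**The concern.** SAP 7.7 is where a reader looks to learn how the safety analysis departs from the protocol. A report writer who relies on it would state that the safety analysis was carried out as planned, when it was reduced in several places.

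The primary endpoint matters most. The MTD rule works on subjects with at least one DLT at a dose level, but a table by PT does not give that number: a subject with two different DLT terms appears in two rows, so the rows cannot be summed to subjects. With no interval, a result such as 0 of 6 can also read as stronger evidence of tolerability than six subjects can provide.

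**Working it through.** **Step 1. Compare the outputs.** The plan states no figure to reproduce here, so the two texts are set side by side.

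| Output | Protocol | SAP | Result |
|---|---|---|---|
| CI on percentages | 8.4: exact, two-sided, 95% | 3 and 7.1.7: number and percentage, no CI | Omitted |
| DLT incidence | 8.1.2: primary endpoint; 8.4: N, n, percentage and CI | 7.1.7: summary by PT | Subject-level incidence by dose level not specified |
| TEAEs | 8.7.2: "Summaries (number and percentage of subjects) of TEAEs by SOC and PT will be provided by cohort, indication, and treatment" | 7.1.6 and 7.1.6.1: by PT, by cohort or dose level | SOC level and indication omitted |
| Compliance | 8.7.1: share of drug taken, "based on returned pill count relative to the amount that was dispensed" | 4.2.1 and 4.2.2: ratio of durations within the DLT window | Pill count omitted |
| Grade 3 or higher laboratory abnormalities | 8.7.3: "Separate listings and summaries will be prepared for laboratory abnormalities that are Grade" 3 or higher | 7.2.1.2: one table of treatment-emergent abnormalities by worst grade | Separate summary and listing omitted; Grade 3 and 4 counts still visible |
| Laboratory change from baseline | 8.7.3: selected tests, at all scheduled time points | 7.2: quantitative and qualitative methods, no table named | Under-specified rather than clearly dropped |

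Protocol 8.7.3 makes shift tables optional, so their absence is not counted.

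**Step 2. Does the CI rule reach the DLT endpoint?** It sits in protocol 8.4, not in 8.7, and the protocol has no CI sentence specific to DLTs. But 8.4 covers categorical summary tables and binary variables in general, DLT incidence is a binary subject-level outcome, and nothing in 8.7 replaces the rule for DLTs. It therefore applies.

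**Step 3. What the interval would show.** Inputs: block size 3 and minimum 6 subjects for an MTD (protocol 3.2.1, SAP 1.2.1); exact, two-sided, 95% (protocol 8.4), so 0.025 in each tail. The DLT counts are illustrative and are not trial results.

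Clopper-Pearson limits for x of n: L solves P(X ≥ x | n, L) = 0.025 and U solves P(X ≤ x | n, U) = 0.025. For x = 0, L = 0 and U = 1 − 0.025^(1/n).

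- 0/3: U = 1 − 0.025^(1/3) = 1 − 0.292 = 0.708. Interval 0 to 70.8%.
- 0/6: U = 1 − 0.025^(1/6) = 1 − 0.541 = 0.459. Interval 0 to 45.9%.
- 1/6 (16.7%): L = 1 − 0.975^(1/6) = 0.004; U solves (1 − U)^6 + 6U(1 − U)^5 = 0.025, giving 0.641. Interval 0.4 to 64.1%. Substituting the unrounded limits back gives 0.025 in each tail.

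The outcomes 0/6 and 1/6 are the two that allow a dose level to be called the MTD. An outcome of 0/3 allows escalation only.

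**The case against.** The other side has five arguments.

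1. *The CI rule is a general convention, while 7.7 answers the protocol's safety section.* Protocol 8.7.2 asks only for number and percentage of subjects with TEAEs, and the SAP matches that. This stands for TEAEs, where CIs are optional. It does not stand for DLTs, because 8.7 has no specific wording that displaces 8.4.
2. *The DLT information is recoverable.* SAP 3 gives percentages, SAP 7.1.7 adds a by-subject DLT listing by cohort, and SAP 4.1 tabulates the DLT-evaluable set by cohort. A reader could rebuild incidence and interval from these. That is true, but the summary of the only primary endpoint should not have to be reconstructed from a listing.
3. *Laboratory severity is not lost.* Correct: the worst-grade table shows Grade 3 and 4 counts, and the listings flag graded values. A reader might infer that severe laboratory findings would go unreported; the documents do not support that. On change from baseline, SAP 3.8.3 uses such a by-visit analysis as an example, so the gap is an unnamed table.
4. *No decision uses an interval.* Correct. Escalation and MTD follow a fixed count rule. A reader might infer that the dose decisions or the primary result itself are compromised; nothing in the documents supports that.
5. *Early termination and a synoptic CSR explain a shorter set.* Protocol 9.2.2 allows an abbreviated report in certain cases, and indication-level tables in a mixed-tumour escalation of up to 44 subjects would be sparse. Adherence is also handled in SAP section 4, outside the section that 7.7 closes, although the protocol places compliance under its safety analysis (8.7.1). All of this can justify fewer tables. It cannot justify saying that nothing changed, and SAP 2.1.2 and 2.1.3 show that the SAP discloses dropped analyses when it chooses to.

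**Conclusion.** The point stands as a mismatch between the SAP's declaration and its content, and as a gap in how the primary endpoint is reported. The clear omissions are the exact CI on DLT incidence, the SOC level and indication breakdown of TEAEs, pill-count compliance, and the separate Grade 3 or higher laboratory summary and listing. Subject-level DLT incidence by dose level and laboratory change from baseline are not specified.

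The practical size lies in the interval. With six subjects, both outcomes compatible with an MTD leave DLT rates above 45% inside the 95% CI (upper limits 45.9% and 64.1%). The limits treat the number of subjects as fixed, which a 3+3 scheme does not strictly satisfy, but this is the method that the protocol prescribes.

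A reader might also want to quote a tighter interval for the full 1000 mg BID cohort (0/20 would give 0 to 16.8%). The protocol does not support that denominator, because section 8.3.1.4 limits the DLT-evaluable set to at most the first six subjects in that cohort. SAP 3.1.4 does not repeat the limit, so the DLT table should state which denominator it uses.

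**What to change.** - In SAP 7.1.7, add the number and percentage of DLT-evaluable subjects with at least one DLT, by dose level, with the two-sided Clopper-Pearson 95% CI. Keep the PT summary as supporting detail.
- Replace the sentence in SAP 7.7 with a list of the protocol safety outputs reduced for the synoptic CSR, each with its reason: SOC level and indication for TEAEs, pill-count compliance, the separate Grade 3 or higher laboratory summary and listing, and laboratory change from baseline if it is not to be produced. Any of these that the sponsor prefers to restore can come off the list.
- CIs on TEAE incidence may be added but are not needed to meet the protocol.
- If the SAP is already final (it carries electronic signatures from July 2021), record these points in the CSR, as SAP 1 provides for later changes.

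The cost is one small table and a paragraph of text. No new data are needed.
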